7.3.2 Withdrawal of informed consent for use of biological samples

If a subject withdraws consent to the use of biological samples, the samples will be disposed of and destroyed, and the action documented.

The Principal Investigator:

- Ensures that biological samples from that subject, if stored at the study site, are immediately identified, disposed of /destroyed, and the action documented
- Ensures the laboratory(ies) holding the samples is/are informed about the withdrawn consent immediately and that samples are disposed/destroyed, the action documented and the signed document returned to the study site
- Ensures that the subject is informed about the sample disposal.

8. DRUG INFORMATION

Pfizer, Inc. manufactures Avelumab. Specific storage, preparation, and other information is contained within the Investigational Product Manual for Active and Placebo MSB0010718C, Avelumab (v.3).

Drug supply will be ordered from Pfizer via the Drug Supply Form.

9. SAFETY ASSESSMENT

9.1 Definition of an adverse event

An adverse event (**AE**) is defined as any **untoward medical occurrence** in a patient or clinical investigation subject following use of avelumab. There does **NOT** need to be a causal relationship between the event and the Pfizer product.

9.2 Definition of serious adverse events

- Results in death;
- Is life-threatening (i.e., causes an immediate risk of death);
- Results in inpatient hospitalization or prolongation of existing hospitalization;
- Results in a persistent or significant disability/incapacity (i.e., substantial disruption in the ability to conduct normal life functions); or
- Considered to be an important medical event

Serious adverse events (SAEs) during pregnancy are defined as follows:

- Spontaneous abortion (includes miscarriage and missed abortion)
- Stillbirth
- Congenital anomaly (including in an aborted fetus, a stillborn infant, or neonate that dies shortly after birth)
- Neonatal death within 1 month of birth
- Infant death that is considered possibly related to intrauterine exposure to avelumab

9.3 Definition of adverse events of special interest

Adverse events of special interest (AESIs) are events specific to the further understanding of the safety profile of avelumab and require close monitoring and rapid communication by the investigator to the sponsor. Avelumab AESIs may be serious or non-serious.

AESIs include immune-mediated reactions such as enterocolitis, dermatitis, hepatotoxicity or hepatitis, endocrinopathy, neuropathy, nephritis and pneumonitis, as well as infusion related reactions, serious allergic reactions and anaphylaxis.

9.4 Infusion related reactions and serious allergic reactions

The frequency of high grade infusion reactions in clinical trials with ICIs is rare. (16, 22, 69-80) A high frequency of mild infusion reactions, was observed with anti-PD-L1 and anti-PD-1 therapy (81).

As with the administration of any foreign protein and/or other biologic agents, reactions following the infusion of MAbs can be caused by various mechanisms, including acute anaphylactic (IgE-mediated) and anaphylactoid reactions against the MAb, and serum sickness. Hypersensitivity reactions as well as infusion-related reactions have been reported with anti-PD-L1 and anti-PD-1 therapy (71).

Acute allergic reactions may occur, may be severe, and may result in death. Acute allergic reactions may include hypotension, dyspnea, cyanosis, respiratory failure, urticaria, pruritis, angioedema, hypotonia, arthralgia, bronchospasm, wheeze, cough, dizziness, fatigue, headache, hypertension, myalgia, vomiting and unresponsiveness. The incidence of high grade (grade ≥ 3) allergic reactions (e.g., anaphylaxis) have an incidence of $\leq 1\%$. (16, 22, 69-80). The

typical onset is within 30 minutes to two hours after the initiation of drug infusion, although symptoms may be delayed for up to 24 hours. The majority of reactions occur after the first or second exposure to the agent, but between 10 and 30 percent occur during subsequent treatments (82).

Guidelines for management of subjects with hypersensitivity (including anaphylactic reaction) and infusion-related reactions are outlined in Section 5.2 and Table 6 (section 5.6).

9.5 Select immune mediated adverse events

- Immune mediated pneumonitis
 - Signs and symptoms of pneumonitis include dyspnea (53%), new or worsening cough (35%), chest pain (7%), and radiographic changes. Up to 33% of patients may be asymptomatic at the onset of pneumonitis. Fatal cases of pneumonitis have occurred in less than 0.5% of cases in clinical trials of PD-1/PD-L1 inhibitor monotherapy. A case series from Memorial Sloan Kettering and the Melanoma Institute of Australia reported a pneumonitis incidence of 3% in patients treated with PD-1 or PD-L1 inhibitor monotherapy, with only 2% of cases being fatal. Most cases are grade 1 to 2 and improve with instituting the recommended therapies (88%). The median time to onset is approximately 2.8 months. (72, 83)
- Immune mediated colitis
 - Signs and symptoms include diarrhea (loose stools) or bowel movements more than usual, blood in stool or dark/tarry/sticky stool or severe abdominal pain/tenderness. (72)
- Immune mediated hepatitis
 - Signs and symptoms include transaminase elevations, elevations in total bilirubin, yellowing of the skin or the whites of the nails, severe nausea or vomiting, right sided abdominal pain, drowsiness, dark or tea colored urine, bleeding or bruising more easily than normal, and feeling less hungry than usual. (72)
- Immune mediated endocrinopathy
 - Signs and symptoms – headaches that will not go away or unusual headaches, extreme tiredness, weight gain and/or weight loss, dizziness or fainting, changes in mood or behavior (e.g., decreased sex drive, irritability or forgetfulness), hair loss, feeling cold, constipation, voice gets deeper, increased thirst, or change in frequency of urination. (72)
- Adrenal crisis
 - Signs and symptoms may include – severe dehydration, hypotension or shock out of proportion to current illness. (72)
- Immune mediated nephritis
 - Signs and symptoms – increase in serum creatinine, decrease in the amount of urine output, blood in the urine, swelling of the ankles, or loss of appetite. (72)
- Immune mediated rash
 - Signs and symptoms – rash, itchiness of the skin, skin blisters, and ulcers in the mouth or other mucous membranes. Signs and symptoms of dermatitis should be considered immune-mediated when on avelumab unless another etiology has been found. (72)
- Immune mediated encephalitis and other immune mediated neurological syndromes
 - Signs and symptoms – headache, fever, tiredness or weakness, confusion or memory problems, sleepiness, hallucinations, seizures or stiff neck. (72)

- Immune mediated myocarditis
 - Signs and symptoms include chest pain, dyspnea, fatigue, myositis with elevated creatinine kinase and cardiac conduction abnormalities. (84) Severe immune mediated myocarditis is a rare event with PD-1 pathway inhibitors, reported in less than 0.10% of treated patients. Review of a large safety database by Bristol Myers Squib that included 20,594 patients treated with nivolumab (a PD-1 inhibitory antibody) or nivolumab + ipilimumab (a CTLA4 inhibitory antibody) found a 0.09% incidence of severe drug related immune mediated myocarditis. This event rate was lower for nivolumab monotherapy at 0.06%. (85)

9.6 Incidence of select adverse events with immune checkpoint inhibitors

Table 10: Incidence of Adverse Events with Immune Checkpoint Inhibitors

Adverse events	CTLA-4 inhibitors	PD-1 or PD-L1 inhibitors
Any high grade (≥ 3) event	20-55%	10-43%
Anemia	8% grade 1-2 3% grade 3-4	0-8% grade 1-2 0-17% grade 3-4
Common adverse events (almost always grade 1-2) include: arthralgia, asthenia, back pain, constipation, decreased appetite, fatigue, fever, musculoskeletal pain, nausea and vomiting.	3-42%	0-34%
Endocrinopathies (e.g., disorders affecting the adrenal, gonadal, pancreas, pituitary or thyroid glands)	Unclear incidence due to variable reporting across trials	Unclear incidence due to variable reporting across trials
Infusion reactions	< 1% grade ≥ 3	< 1% grade ≥ 3
High grade diarrhea and colitis	5-17% (intestinal perforation had an incidence of 1% across studies and death was 0.8%)	0-5%
Myocarditis	N/A	0.06% grade ≥ 3
Nephritis	Rare	0-3% grade ≥ 3
Neutropenia	Rare	Rare
Pneumonitis (usually mild)	5% grade 1-2 0-3% grade ≥ 3	1-5% grade 1-2 0-3% grade ≥ 3
Rash (usually mild)	18-40% grade 1-2	0-26% grade 1-2
Severe dermatologic reactions (including bullous pemphigoid, full thickness ulceration, hemorrhagic or	2.5%	Rare

necrotic rash, Steven Johnson syndrome and toxic epidermal necrolysis)		
Other rare events (including duodenitis, gastritis, hematologic events, hypercalcemia, neurologic events, pancreatitis, pleural effusion, pneumonia, polymyalgia rheumatica, sarcoidosis, systemic inflammatory response syndrome, uveitis and vasculitis)	Rare	Rare
Thrombocytopenia	Rare	0-17% grade 1-2
Transaminitis (usually mild)	1-10% grade ≥ 3	0-5% grade ≥ 3

Grade 1 = mild, grade 2 = moderate, grade 3 = severe, grade 4 = life threatening and grade 5 = death. Rare adverse events are limited to case reports and are generally < 1% across studies. Neurologic adverse events include things such as (e.g., abducens or facial nerve palsy, autoimmune neuropathy, encephalitis, Guillain-Barre Syndrome, motor dysfunction, myasthenia gravis or transverse myelitis). (16, 22, 69-80, 84-85)

9.7 Attribution/recording of adverse events and serious adverse events

All adverse events, regardless of relatedness, will be reported on the appropriate case report forms. Adverse events will be described by nature of the event, the duration (start and stop dates and times), grade, treatment, relation to study drug, or if unrelated then the cause will be reported, the clinical course of the patient and the final outcome of the event.

The descriptions and grading scales found in the NCI Common Terminology Criteria for Adverse Events (CTCAE) version 4.03 will be utilized for all toxicity reporting. A copy of the CTCAE version 4.03 can be downloaded from the CTEP website.

Each event should be evaluated for its relatedness to participation in the research:

- Definite: The AE is *clearly related* to the study treatment.
- Probable: The AE is *likely related* to the study treatment.
- Possible: The AE *may be related* to the study treatment.
- Unlikely: The AE is *doubtfully related* to the study treatment.
- Unrelated: The AE is *clearly NOT related* to the study treatment.

9.8 Study recording period and follow-up for adverse events

AEs and SAEs will be recorded from the time of first treatment with Avelumab, throughout the treatment period and including the follow-up period (90 days after RC). During the course of the study all AEs and SAEs will be proactively followed up for each subject. Every effort will be made to obtain a resolution for all events, even if the events continue after discontinuation/study completion.

If a subject discontinues treatment for reasons other than disease progression, and therefore continues to have tumor assessments, drug or procedure-related SAEs must be captured until

the patient is considered to have confirmed PD and will have no further tumor assessments. The investigator is responsible for following all SAEs until resolution, until the subject returns to baseline status, or until the condition has stabilized with the expectation that it will remain chronic, even if this extends beyond study participation.

9.9 Follow-up of unresolved events

Any AEs that are unresolved at the subject's last visit in the study are followed up by the investigator for as long as medically indicated, but without further recording in the adverse event log. After 90 days post-RC, only subjects with ongoing investigational product-related SAEs will continue to be followed for safety.

Pfizer retains the right to request additional information for any subject with ongoing AE(s)/SAE(s) at the end of the study, if judged necessary.

9.10 Post-study events

After the subject has been permanently withdrawn from the study, there is no obligation for the investigator to actively report information on new AEs or SAEs occurring in former study subjects after the 90-day post-RC safety follow-up period for patients treated with avelumab. However, if the investigator learns of any SAEs, including death, at any time after the subject has been permanently withdrawn from study, and he/she considers there is a reasonable possibility that the event is related to study treatment, the investigator will notify Pfizer immediately.

9.11 Reporting of Adverse Events

The investigator primary responsibilities in the safety reporting are to identify and follow-up on SAEs experienced by participants in the study and to forward the information to the local regulatory authorities and Pfizer, as required by local regulations (for regulatory reporting) and IIR agreement (for reporting to Pfizer).

The following reportable events must be submitted to Pfizer within 24 hours of knowledge of the event (or immediately for death or life-threatening events) using the provided Investigator-Initiated Research Serious Adverse Event Form (IIR SAE) with the Pfizer Reportable Events Fax Cover Sheet with each SAE submission.

- Serious Adverse Events
- Exposure during Pregnancy or Breastfeeding (even if not associated with an adverse event)
- Occupational exposure (even if not associated with an adverse event)
- Potential drug-induced liver injury (Hy's Law cases): These events are considered important medical events and should be reported as SAEs.

Detailed guidance on the safety reporting is provided in the Safety Reporting Reference Manual.

Contact information for submission of reportable events to Pfizer:

- Fax: Pfizer U.S. Clinical Trial Department, [contact].

or

- E-mail: [contact], specifying:
 - PROTOCOL:
 - SUBJECT:
 - SITE/PI:
 - SAE/ONSET:

Serious adverse events are to be reported to the Baylor College of Medicine (BCM) Institutional Review Board (IRB) according to the board's reporting requirements and required time frame.

Any event that is reportable to the BCM IRB must also be reported to the Dan L Duncan Comprehensive Cancer Center (DLDCCC) Data Review Committee (DRC) via the Patient Safety Officer at [contact].

9.12 Reporting of Deaths

All deaths that occur during the study, or within the protocol-defined 90-day post-RC safety follow-up period must be reported as follows:

- Death that is clearly the result of disease progression should be documented but should not be reported as an SAE.
- Where death is not due (or not clearly due) to progression of the disease under study, the AE causing the death must be reported as a SAE within 24 hours. The

report should contain a comment regarding the co-involvement of progression of disease, if appropriate, and should assign main and contributory causes of death.

- Deaths with an unknown cause should always be reported as a SAE.

Deaths that occur following the protocol-defined 90-day post-RC safety follow-up period will be documented as events for survival analysis, but will not be reported as a SAE.

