3.2 Study Schema

3.3 Study Oversight for Safety Evaluation

In metastatic UCC, the high grade treatment related adverse event rate with avelumab is approximately 10% and the rate of serious adverse events (SAEs) is 5-10%. (54-59)

Treatment may be put on hold, and pending full review of the data, the study may be stopped if any of the following criteria are met:

- Two (2) avelumab-related SAEs are reported
- At least 2 subjects experience a similar unanticipated avelumab-related AE

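### Section 9.12 keeps every death after the 90-day post-cystectomy period out of SAE reporting, with no exception for the possibly avelumab-related deaths that 9.10 requires to be notified at once

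*Protocol*

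**What the plan says.** Four parts of the protocol bear on a death that occurs after the 90-day post-RC period.

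- **Section 9.12 (deaths).** Inside the period, a death that is not, or not clearly, due to progression is an SAE with a 24-hour limit. After it, deaths "will be documented as events for survival analysis, but will not be reported as a SAE". Relatedness is not mentioned, and there is no reference to another section.
- **Section 9.10 (post-study events).** After the same 90 days there is no duty to report new events actively. An exception follows, which applies "if the investigator learns of any SAEs, including death, at any time after the subject has been permanently withdrawn from study". It depends on the investigator's view of causality, and the resulting duty is worded thus: "he/she considers there is a reasonable possibility that the event is related to study treatment, the investigator will notify Pfizer immediately".
- **Sections 9.8 and 9.9.** For subjects who stop treatment for reasons other than progression, 9.8 has drug- or procedure-related SAEs captured until confirmed progression, with no 90-day limit. Section 9.9 keeps subjects with an ongoing product-related SAE under safety follow-up past day 90.
- **Sections 9.2, 9.11 and 3.3.** An event that "Results in death" is an SAE by definition. Section 9.11 sends SAEs to Pfizer "within 24 hours of knowledge of the event (or immediately for death or life-threatening events") and to the IRB under the board's own requirements, and adds: "Any event that is reportable to the BCM IRB must also be reported to the Dan L Duncan Comprehensive Cancer Center" DRC. The first criterion in 3.3 for a possible hold or stop is "Two (2) avelumab-related SAEs are reported".

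**The concern.** A late death that may be due to avelumab falls under two instructions at once: tell Pfizer immediately (9.10), and do not report it as an SAE (9.12). Section 9.12 is the section on deaths, so it is the one that staff are likely to open when a patient dies, and nothing in it points back to 9.10.

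Sites will learn of late deaths. Section 7.2.5 follows patients who are evaluable for secondary endpoints about every 3 months, by visit or telephone, up to 2 years after RC. What is at stake is whether a possible treatment-related death reaches those who oversee safety while other patients are being enrolled or dosed. The primary endpoint and the disease-free survival analysis are not affected, since 9.12 still records the death as a survival event.

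**Working it through.** The point compares reporting rules, so there is no stated figure in the protocol to reproduce. The sections are set side by side first. The day arithmetic then shows whether the situation can arise during recruitment.

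**1. One event under each section.** Take a patient who dies after day 90 post-RC, where the investigator sees a reasonable possibility of relation to avelumab.

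| Section | Instruction |
|---|---|
| 9.2 | The event is an SAE |
| 9.10 | Notify Pfizer immediately; IRB and DRC not named |
| 9.8, 9.9 | A related SAE may still be under capture or follow-up |
| 9.12 | Survival event only; not an SAE report |
| 9.11 | IRB receives SAEs; DRC receives what is IRB-reportable |

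If 9.12 prevails, no SAE report is made and the route in 9.11 to the IRB and DRC does not start. If 9.10 prevails, Pfizer is told, but the protocol still does not say that the IRB or DRC is. Section 9.10 is also worded for subjects permanently withdrawn, whereas under 12.3 the study ends at 90 days after RC and most patients will simply complete it. Its reach over completers is therefore unclear.

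**2. When the period closes.** Section 7.1 places RC on day 41 to 64.

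- Earliest: 41 + 90 = day 131; 131 / 30.44 = 4.3 months after first dose.
- Latest: 64 + 90 = day 154; 154 / 30.44 = 5.1 months.

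**3. Overlap with enrolment and dosing.** Section 12.3 gives about 12 months of recruitment, taken as 365 days. Assume that the first patient starts on day 1 and the last on day 365, whose third dose (study day 29) falls on day 365 + 28 = 393.

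- Enrolment left after the first patient's period closes: 365 − 154 = 211 to 365 − 131 = 234 days.
- Time left until the last patient's third dose: 393 − 154 = 239 to 393 − 131 = 262 days.

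These are upper bounds, because the overlap shrinks by one day for each day later that a patient starts. It reaches zero for patients starting after about 7.9 to 8.6 months (239 / 30.44 and 262 / 30.44).

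**4. How likely is such a death?** The protocol gives no rate for late, related deaths. Section 1.9.1 says immune reactions lead to death in rare cases. Section 9.5 puts fatal pneumonitis below 0.5% in trials of PD-1/PD-L1 monotherapy, with a median onset of about 2.8 months, which is before the period closes. The event is possible but should be rare.

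**5. Weight of one event under 3.3.** This is an illustration only. Section 3.3 gives an SAE rate of 5–10%. Take it as the chance p of one related SAE per patient, independent across 10 patients.

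- P(at least 2 of 10) = 1 − (1 − p)^10 − 10p(1 − p)^9 = 0.086 at p = 0.05 and 0.264 at p = 0.10.
- If one event already counts, P(at least 1 of the other 9) = 1 − (1 − p)^9 = 0.370 and 0.613.

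The first criterion is thus sensitive to whether a single event is counted. The calculation says nothing about how often a late related death would be that event.

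**The case against.** The strongest answer is that the sections can be read together. Section 9.12 sets the default for late deaths, most of which would presumably be due to recurrence or comorbidity, and 9.10 is the specific exception. Notifying Pfizer and filing an SAE report are different acts, so both could be obeyed. Section 9.11 also defers to a safety reporting manual, the research agreement and the IRB's requirements, none of which is at hand. The principal investigator holds all oversight (section 12), and the DRC reviews toxicities at least yearly (section 14).

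Much of this stands. A site that applies 9.10 as an exception will tell Pfizer. It is not a full answer, because 9.12 is unqualified, 9.10 is worded for withdrawn subjects and names Pfizer alone, and the IRB and DRC route in 9.11 runs through the SAE report that 9.12 excludes.

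A reader might infer more than the text supports:

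- **That a late related death would drop out of the stopping criteria.** Section 3.3 is discretionary, sets no time limit and does not define what counts as reported; a notification under 9.10 might qualify. Its second criterion, "At least 2 subjects experience a similar unanticipated avelumab-related AE", does not depend on SAE reporting at all.
- **That 9.11 and 9.12 set incompatible time limits for a fatal SAE within the 90 days.** Immediate reporting satisfies both. The wording differs, but no one is forced to breach either.
- **That about 21 of the 24 months of follow-up (24 less 3), or 7 months of recruitment, are exposed.** For patients still being enrolled or dosed, only the overlap in time matters. The 211 to 234 days of enrolment apply only to a patient who starts on day 1.

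**Conclusion.** The conflict between 9.12 and 9.10 is real and stands in the current text. Read literally, 9.12 lets a late, possibly avelumab-related death be filed as a survival event only, and the IRB and DRC might then not receive it. For early patients this could coincide with continuing enrolment, since the period closes on about day 131 to 154 against some 12 months of recruitment.

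Non-reporting is a possible consequence, not a certain one: it requires staff to follow 9.12 over 9.10. Any effect on 3.3 is less certain still. The overlap figures assume a first patient on day 1 and a 365-day recruitment period. Given the expected rarity of such deaths and the target of 10 evaluable patients, the point is moderate to minor.

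**What to change.** 1. Limit the last sentence of 9.12 to deaths without a reasonable possibility of relation to avelumab, and refer all other late deaths to 9.10 and 9.11.
2. In 9.10, make clear whether it covers subjects who completed the study as well as those withdrawn, and whether these events also go to the IRB and DRC.
3. Have the sponsor clarify whether late related events are among those reported for 3.3. How that criterion should operate is for the sponsor to decide.
4. Optionally, align the wording of the time limits for fatal events in 9.11 and 9.12.

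The cost is a few sentences in a protocol amendment, with no new data, visits or patients.
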